6.0 Inclusion and Exclusion Criteria

NOTE: If your study is more than minimal risk, you must also upload a copy of your inclusion/exclusion checklist (with space for specific subject values) to be completed at time of enrollment of each subject.

6.1 Describe, in bullet points, the criteria that define who will be included in this study:

Response: *Age of 18-30 years
*BMI of 18-29.9
*Pregnancy

PROTOCOL TITLE:

6.2 *Describe, in bullet points, the criteria that define who will be excluded from this study:*

Response: *Those with a history of significant illness including diabetes, renal, liver or cardiovascular disease, malnutrition, GI disease (including IBS, IBD, chronic constipation or diarrhea), mental illness (i.e. depression, bipolar disorder)
*Those adhering to a vegetarian or vegan diet.
*Those having taken antibiotics within 1 month of starting the study

6.3 *Describe how individuals will be screened for eligibility. Upload all relevant screening documents with your submission (screening protocol, script, questionnaire). Identify who will certify that subjects meet eligibility requirements.*

Response: We will have 2 layers of screening during recruitment. The initial screening which will be Qualtrics-based and done remotely (accessed from a QR code on the paper announcements or as a link in the email announcements) and will immediately exclude potential participants if they don't meet the basic eligibility criteria (screening survey attached to this protocol). This will be done anonymously if they don't pass the survey. If they do pass the survey, individuals will submit their name, email address and phone number so that they can be scheduled for a follow up in-person screening. The second screen will occur in person. The in-person interview will be conducted by a dietetic intern from the Dietetic Internship of the Division of Nutrition at Stony Brook University in room 206 of the Earth and Space Science (ESS) building at Stony Brook University (private office) or in room 3-064C in the HSC building on the East side of the Stony Brook University campus (conference room located in the office suite of the Division of Nutrition). During this interview, interested participants will be provided greater detail of the study design (i.e. told that they must only consume the meals they are provided and must pick up their daily meals each day for the period of the study) to determine whether they are still willing to participate after receiving this information. They will also be asked to complete a health questionnaire (health questionnaire attached to this protocol). Based on inclusion and exclusion criteria the dietetic intern will enroll subjects and obtain consent. Dietetic interns will then teach the subjects how to complete the Qualtrics-based food log and conduct the indirect calorimetry study.

6.4 *Indicate whether you are specifically recruiting or targeting any of the following special populations in your study using the checkboxes below. (You will be asked for additional information in Section 7 if you check any of these boxes)*

Response: N/A

PROTOCOL TITLE:

- Adults unable to consent
- Minors (under 18 years old)
- Pregnant women
- Prisoners

6.5 Indicate if you will include minorities (American Indians, Alaskan Native, Asian, Native Hawaiian, Pacific Islander, Black [not of Hispanic origin] and Hispanic) as Federal mandates require that you include minorities unless you can justify their exclusion

Response:

- Yes
- No, Justify:

6.6 Indicate whether you will include non-English speaking individuals in your study. Provide justification if you will specifically exclude non-English speaking individuals. Review <http://research.stonybrook.edu/human-subjects-standard-operating-procedures/policy-non-english-speakers-research-subjects> for SBU policy on inclusion of non-English speakers. Upload any translated materials (consent, questionnaires, etc).

Response: Since our subject population will be undergraduate, graduate or medical/dental students, therefore all participants will have a working knowledge of English.

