Response: We will have 2 layers of screening during recruitment. The initial screening will be Qualtrics-based and done remotely upon a potential subject viewing an advertisement and accessed from a QR code on the paper announcements or as a link in the email announcements. This initial screen will exclude potential participants if they don't meet the basic eligibility criteria (screening survey attached to this protocol). This will be done anonymously if they don't pass the survey. We predict that about 40 people will take the screening survey and 50% of the individuals who take this initial survey will not be eligible. The second screen will occur in person and consist of individuals completing a health questionnaire and being provided a detailed description of study design and requirements to participate in the study. The detailed description will include a review of the two choices of menus/ingredients for each phase of the study, followed by written agreement by the subject to eat the foods provided. Of the 20 people remaining who will undergo the in-person screening, we predict that approximately 20% of those individuals will be excluded, resulting in our goal of enrolling 14 people to result in 10 people having completed the entire study.

5.4 Justify the feasibility of recruiting the proposed number of eligible subjects within the anticipated recruitment period. For example, how many potential subjects do you have access to? What percentage of those potential subjects do you need to recruit?
Response: In light of the fact that we will be targeting SBU students for recruitment, there is a pool of approximately 25,000 individuals. Therefore we believe that reaching our goal of enrolling 14 will be feasible.

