8.0 Eligibility Screening

8.1 Describe screening procedures for determining subjects' eligibility. Screening refers to determining if prospective participants meet inclusion and exclusion criteria.

Include all relevant screening documents with your submission (e.g. screening protocol, script, questionnaires) as attachments.

Response: *We will have 2 layers of screening during recruitment. The initial screening which will be Qualtrics-based and done remotely (accessed from a QR code on the paper announcements or as a link in the email announcements) and will immediately exclude potential participants if they don't meet the basic eligibility criteria (screening survey attached to this protocol). This will be done anonymously if they don't pass the survey. If they do pass the survey, individuals will submit their name, email address and phone number so that they can be scheduled for a follow up in-person screening. The second screen will occur in person. The in-person interview will be conducted by a dietetic intern from the Dietetic Internship of the Division of Nutrition at Stony Brook University in room*

PROTOCOL TITLE:

206 of the Earth and Space Science (ESS) building at Stony Brook University (private office). During this interview, interested participants will be provided greater detail of the study design (i.e. told that they must only consume the meals they are provided and must pick up their daily meals each day for the period of the study) to determine whether they are still willing to participate after receiving this information. They will also be asked to complete a health questionnaire (health questionnaire attached to this protocol). They will be asked if they are pregnant or are planning to become pregnant. Based on inclusion and exclusion criteria the dietetic intern will enroll subjects and obtain consent.

N/A: There is no screening as part of this protocol.

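### Pregnancy is listed as an inclusion criterion and not as an exclusion, and the screening question about current or planned pregnancy has no stated consequence

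*Combined protocol and SAP*

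**What the plan says.** The response in section 6.1 (inclusion) reads "Response: *Age of 18-30 years *BMI of 18-29.9 *Pregnancy". The third bullet stands alone, with no qualifier such as a negation.

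Section 6.2 (exclusion) also has three bullets: a history of significant illness, a vegetarian or vegan diet, and recent antibiotic use ("Those having taken antibiotics within 1 month of starting the study"). None refers to pregnancy.

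Section 8.1 adds a question at the in-person screen and goes straight on to enrolment. Candidates are "asked if they are pregnant or are planning to become pregnant. Based on inclusion and exclusion criteria the dietetic intern will enroll subjects". Section 6.3 describes the same interview without the pregnancy question and has the same enrolment rule: "Based on inclusion and exclusion criteria the dietetic intern will enroll subjects and obtain consent".

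On recruitment, section 5.4 says "we will be targeting SBU students for recruitment, there is a pool of approximately 25,000 individuals". Section 5.3 predicts that "about 40 people will take the screening survey and 50% of the individuals who take this initial survey will not be eligible", and then: "Of the 20 people remaining who will undergo the in-person screening, we predict that approximately 20% of those individuals will be excluded". The enrolment goal is 14.

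**The concern.** The inclusion list, the exclusion list and the screening question do not combine into one rule. Asking about pregnancy suggests that the answer matters to eligibility, but the only listed criterion that uses it points towards entry. For planned pregnancy there is no criterion in either list.

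This is not background text. Sections 6.3 and 8.1 both direct the intern to enrol on the two lists. Applied as written, a candidate who reports being pregnant meets an inclusion criterion, a candidate who is not pregnant fails one, and a candidate planning a pregnancy has no rule at all. Participants eat only study meals for 5 to 6 weeks at two set protein levels, so who may enter is a participant-protection question.

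**Working it through.** **1. The lists, counted by bullet**

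| Item | 6.1 inclusion (3 bullets) | 6.2 exclusion (3 bullets) | 8.1 screening |
|---|---|---|---|
| Current pregnancy | 1 of 3 | 0 of 3 | Asked; no consequence stated |
| Planned pregnancy | 0 of 3 | 0 of 3 | Asked; no consequence stated |

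Planned pregnancy therefore appears in 0 of 6 bullets. If the pregnancy bullet were simply moved from 6.1 to 6.2, the count for planned pregnancy would still be 0 of 6.

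**2. The plan's own screening projection (section 5.3)**

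- Inputs: about 40 survey takers, 50% ineligible at the survey, about 20% excluded in person, goal of 14 enrolled.
- Pass the survey: 40 × (1 − 0.50) = 20, which matches the plan's 20.
- Pass the in-person screen: 20 × (1 − 0.20) = 16, against the stated goal of 14.

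**3. What the literal reading would require**

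Anyone who passes both screens must meet every inclusion criterion, whichever screen applies it. If pregnancy were required, all who pass would have to be pregnant:

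- With 14 enrolled: 14 / 40 = 35% of survey takers.
- With 16 passing: 16 / 40 = 40% of survey takers.

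The documents give no pregnancy rate for the student pool and none is assumed. This is only a plausibility check: the literal reading does not fit open recruitment of students aged 18 to 30.

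**4. Does another section settle it?**

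- Section 6.4, on targeting special populations (pregnant women are one printed option), carries the typed response N/A. This sits badly with pregnancy as an entry requirement, but it states no rule on whether a pregnant candidate may enter.
- Section 7.1 prints both options, and the tick marks cannot be read, so it is not used either way.
- Section 19.1 (withdrawal) does not mention pregnancy.
- Section 20.6 (risk to an embryo or fetus) is answered N/A and gives no eligibility rule.

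No readable section states what follows from the answer to the 8.1 question.

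**5. Power**

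The plan's figure (10 completers, 0.996 SD, paired t-test, 5%) gives a power of 0.800 with the exact two-sided calculation. Nothing in this point changes it.

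**The case against.** The strongest reply is that this is an obvious slip. Requiring pregnancy would bar every man and nearly all of the student pool, no intern would apply it, and the N/A in section 6.4 shows what was meant. On that view the 35% to 40% figure measures only how implausible a reading is that nobody holds. This is fair as far as it goes: a misplaced exclusion is the likeliest explanation, and the percentage should be taken as no more than a plausibility check. But seeing that the text is wrong does not supply the rule, and correcting the bullet's position leaves planned pregnancy unaddressed.

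A second reply is that section 8.1 never calls planned pregnancy a criterion, and that a shorter parallel description in 6.3 is not a contradiction. The point about 6.3 stands: its omission is not taken as cancelling the 8.1 question. On planned pregnancy, an eligibility screen that asks a question should say what the answer does, even if that is nothing.

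Third, the plan rates overall risk as minimal and answers 20.6 N/A, so no hazard in pregnancy is shown. That is correct, and no specific harm is claimed here. The safety point is only that the protocol does not say who is admitted.

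Fourth, the screening survey and the health questionnaire were not available and may state a rule. They may, and nothing is claimed about them. They should apply the protocol's criteria, however, and cannot correct them. Finally, strike-through marks elsewhere in the text are captured unevenly, so the absence of one on this bullet is not relied on.

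**Conclusion.** The concern holds. As written, pregnancy is one of three conditions for entry and none of three grounds for exclusion, planned pregnancy is in none of the six bullets, and section 8.1 asks about both with no stated consequence. The defect is in the operative eligibility text and must be fixed before the lists are used to enrol anyone.

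Confidence is high for what the text says. That the bullet is a misplaced exclusion is an inference from the 8.1 question, the typed 6.4 response and the recruitment plan; it is not established. The conclusion assumes that the protocol lists, and not the unseen attachments, define eligibility, as sections 6.3 and 8.1 indicate. There is no effect on sample size, power or the paired analysis.

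**What to change.** Reconcile sections 6.1, 6.2 and 8.1 so that they state one eligibility rule covering both current and planned pregnancy, and state in 8.1 what each answer leads to. Carry the same screening text into 6.3. Then check sections 6.4, 7.1 and 20.6, the screening survey and the health questionnaire against that rule and make them agree. Which rule is right is for the investigator and the ethics board, and this review does not propose one.

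The cost is editing one bullet and one or two sentences, plus a consistency check of four sections (6.3, 6.4, 7.1 and 20.6) and two attachments. Design, sample size and analysis do not change.

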7.0 Vulnerable Populations

7.1 For research that involves pregnant women, review, complete and upload Supplemental Form A: Pregnant Women, Fetuses, Non-Viable Neonates , or Neonates of Uncertain Viability.

- Confirmed
- N/A: This research does not involve pregnant women.

7.2 For research that involves neonates of uncertain viability or non-viable neonates, review, complete and upload Supplemental Form A: Pregnant Women, Fetuses, Non-Viable Neonates, or Neonates of Uncertain Viability.

- Confirmed
- N/A: This research does not involve non-viable neonates or neonates of uncertain viability.

PROTOCOL TITLE:

7.3 For research that involves prisoners, review, complete and upload Supplemental Form H: Prisoners

- Confirmed
- N/A: This research does not involve prisoners.

7.4 For research that involves minors (under 18 years), review, complete and upload Supplemental Form F: Minors

- Confirmed
- N/A: This research does not involve persons who have not attained the legal age for consent to treatments or procedures (“children”).

7.5 For research that involves adults who cannot consent for themselves, you will be asked additional information in Section 25 (“Informed Consent”)

- Confirmed
- N/A: This research does not involve this population

7.6 Consider if other specifically targeted populations such as students, employees of a specific firm, or educationally or economically disadvantaged persons are vulnerable. Provide information regarding their safeguards and protections, including safeguards to eliminate coercion or undue influence.

Safeguards include:

- N/A

8.0 Eligibility Screening

8.1 Describe screening procedures for determining subjects' eligibility. Screening refers to determining if prospective participants meet inclusion and exclusion criteria.

Include all relevant screening documents with your submission (e.g. screening protocol, script, questionnaires) as attachments.

Response: *We will have 2 layers of screening during recruitment. The initial screening which will be Qualtrics-based and done remotely (accessed from a QR code on the paper announcements or as a link in the email announcements) and will immediately exclude potential participants if they don't meet the basic eligibility criteria (screening survey attached to this protocol). This will be done anonymously if they don't pass the survey. If they do pass the survey, individuals will submit their name, email address and phone number so that they can be scheduled for a follow up in-person screening. The second screen will occur in person. The in-person interview will be conducted by a dietetic intern from the Dietetic Internship of the Division of Nutrition at Stony Brook University in room*

PROTOCOL TITLE:

206 of the Earth and Space Science (ESS) building at Stony Brook University (private office). During this interview, interested participants will be provided greater detail of the study design (i.e. told that they must only consume the meals they are provided and must pick up their daily meals each day for the period of the study) to determine whether they are still willing to participate after receiving this information. They will also be asked to complete a health questionnaire (health questionnaire attached to this protocol). They will be asked if they are pregnant or are planning to become pregnant. Based on inclusion and exclusion criteria the dietetic intern will enroll subjects and obtain consent.

N/A: There is no screening as part of this protocol.

9.0 Recruitment Methods

N/A: This is a records review only, and subjects will not be recruited. NOTE: If you select this option, please make sure that all records review procedures and inclusion/exclusion screening are adequately described in other sections, including date range for records that will be reviewed.

9.1 Describe source of subjects: When, where, and how potential subjects will be recruited.

NOTE: Recruitment refers to how you are identifying potential participants and introducing them to the study. These may include, but are not limited to: ResearchMatch.org, physician referral, Office of Clinical Trials database, West Campus departmental pools, reviewing medical charts, Research Participant Groups/help groups, advertising companies, call centers, in person announcements / presentations

Response: The study will be advertised on the weekly 'Campus Announcements' email blast, emails sent via student group listservs (e.g. medical students and student clubs) posted in academic buildings, residence halls, cafeterias and locations of student activity.

9.2 Describe how you will protect the privacy interests of prospective subjects during the recruitment process.

NOTE: Privacy refers to an individual's right to control access to him or herself. This is NOT asking about confidentiality of data.

Response: Recruitment flyers and email blasts will be distributed via public venues and inclusive list-serve groups.

9.3 Identify/describe any materials that will be used to screen/recruit subjects and upload copies of these documents with the application. They may include, but are not

PROTOCOL TITLE:

limited to Telephone scripts for calling, flyers, Questionnaires, Posters, Letters or written material to be sent or emailed, pamphlets, posted advertisements, email invitations.

Response: The study will be advertised as text in the weekly email announcements (text attached) and as a paper flyer posted around campus (flyer attached). An initial screening questionnaire will be Qualtrics-based and completed remotely (accessed from a QR code on the paper announcements or as a link in the email announcements) and will immediately exclude potential participants if they don't meet the basic eligibility criteria (screening survey attached). A health questionnaire will be provided at the in-person interview to assess basic health status and medications (questionnaire attached).

10.0 Research Procedures

Provide a detailed description of all research procedures or activities being performed on the research subjects. **This should serve as a blueprint for your study and include enough detail so that another investigator could pick up your protocol and replicate the research.** For studies that have multiple or complex visits or procedures, consider the addition of a schedule of events table in in your response. Be sure to include:

- Procedures being performed to monitor subjects for safety or to minimize risks.
- All drugs and devices used in the research and the purpose of their use, and their regulatory status

Response: After providing consent, subjects will undergo an indirect calorimetry test, which involves breathing through a disposable, single-use mouth piece into a machine that estimates calorie needs based on oxygen consumed and CO₂ produced. Then subjects will be instructed on how to keep a 3-day food record and complete the Qualtrics survey designed for this purpose within 2 weeks of consenting. Dietetic interns will calculate nutrient content of the participants' typical diet, based on the 3-day, Qualtrics-based food/beverage log, using Food Processor software. Meals for the acclimation period will be created to mimic the participants' typical diet (daily calories and percent of calories from carbohydrate, protein and fat), as well as to meet their calorie needs per the indirect calorimeter test, for the first 7-9 days of the study (Figure 1). High protein diets (2g/kg/day) will then be devised and provided for the next 14-16 days.

Following this period, low protein diets (0.8g/kg/day) will be devised and provided for the next 14-16 days (Figure 1). Fat content will be modulated to keep diets isocaloric while keeping carbohydrate content stable. Participants will choose between two 3-day cycle menus for each feeding phase. Meals will be prepared by [name], RD, Chef in a metabolic kitchen housed in SBU's Business Incubator at Calverton with the help of SBU dietetic interns. Meals will be prepared in batches, packaged and frozen at the incubator, then transported in a cooler with thermometers by members of the Nutrition Division to the Food Service Department at SBU Hospital. Meals will be kept frozen in freezers until the day they are provided to participants. Each day of the feeding period, dietetic interns will take all meals for all participants for that day from the freezers and place them in a cooler with a thermometer to bring them to a campus dining area. Logs of temperatures of coolers will be maintained daily, with temperatures checked every hour.

PROTOCOL TITLE:

In order to provide meals, participants will come to room 3-064C in the HSC building on the East side of the Stony Brook University campus (conference room located in the office suite of the Division of Nutrition) ~~a semi-private area on the 2nd floor of the Student Activity Center~~ between 8:30-11AM to eat breakfast onsite and pick up other meals and snacks for the rest of the day, from a dietetic intern. Participants will be provided a closed envelope containing a form that will list their participant ID# and age in which they'll sign in and indicate if they've begun any new medications or been diagnosed with a disease since starting the study (form attached). Additionally, every Monday and Thursday, participants will be weighed using a digital scale in a ~~private area within the Division of Nutrition Suite on the 2nd floor of the Student Activity Center~~, in order to track changes in body weight while on the study. If weight changes greater than 2% of baseline, calorie content of the meals will be modified to avoid further weight changes. Food for the rest of the day will be provided in an insulated bag containing frozen cold packs and participants will be instructed to keep lunch and dinner in the insulated bag or a refrigerator until eaten. They will be instructed to heat the respective meals in a microwave until hot, prior to consumption. They will be instructed to take a picture of each meal before and after eating and upload the pictures via a Qualtrics-based survey, in order for the study team to estimate how much food has been eaten at each meal. Although participants will be instructed to only eat the food and beverages provided for the study, they will log any consumption of food or beverages not provided for the study via this same Qualtrics-based survey. Consumption of water, black coffee and tea will not be logged.

During days 7-9, 24-26 and 41-43 (Figure 1) participants will provide a stool sample to be placed into a sterile container (provided by the study team) then placed into an opaque brown paper bag and brought to the Division of Nutrition Suite student health services within 1 hour, where it will be kept ~~cold in a cooler until refrigerated until picked up by the study team to be~~ stored at -80°C. On the same day as providing ~~At the same time~~ the stool sample ~~is delivered~~, blood will be drawn by a phlebotomist at Student Health Services to generate plasma. An order for the blood draw will be placed by a physician at Student Health Services. The physician will not have any interaction with the study subject. After the blood draw, the phlebotomist at Student Health Services will call and email a member of the [name] Lab to report the sample collection and samples will be kept at 4°C until picked up. ~~Stool and p~~lasma samples will be picked up by a member of the [name] Lab within 1 hour of being contacted. Plasma will be distributed into 2mL screw cap tubes in 4 equal aliquots and ~~stool sample will be cut in half and stored in two 50mL tubes and all samples will be~~ placed into a -80°C freezer until analysis. If a participant provides samples in the earlier part of the collection period (e.g. day 7) they may proceed immediately to the next phase of the study.

[figure not shown]

Figure 1. Experimental design.

PROTOCOL TITLE:

10.1 Describe what data, including long-term follow-up, will be collected.

NOTE: For studies with multiple data collection points or long-term follow up, consider the addition of a schedule or table in your response.

Response: Primary endpoints:

Circulating metabolite levels in blood

Fecal microbiota profiling by 16S rRNA analysis & metatranscriptomics

Fecal metabolite levels

☐ List, and upload, any instruments or measurement tools used to collect data (e.g. survey, scripts, questionnaire, interview guide, validated instrument, data collection form).

Response: These documents have been uploaded.

10.2 Describe any source records that will be used to collect data about subjects (e.g. school records, electronic medical records) and include the date range for records that will be accessed..

Response: N/A

10.3 Indicate whether or not the results for individual subjects, such as results of investigational diagnostic tests, genetic tests, or incidental findings will be shared with subjects or others (e.g., the subject's primary care physician) and if so, describe how these will be shared.

Response: N/A

10.4 Indicate whether or not generalized study results will be shared with subjects or others, and if so, describe how these will be shared.

Response: N/A

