2.0 Scientific/Safety Endpoints

2.1 *Describe the scientific endpoint(s), the main result or occurrence under study.*

NOTE: Scientific endpoints are outcomes defined before the study begins to determine whether the objectives of the study have been met and to draw conclusions from the data. Include primary and secondary endpoints. Some example endpoints are: reduction of symptoms, improvement in quality of life, or survival. Your response should not be a date.

Response:

To determine whether reducing protein intake alters:

Circulating metabolites as determined by targeted metabolite profiling of blood.

Fecal metabolome as determined by targeted metabolite profiling.

Fecal microbiota as determined by 16S rRNA and metatranscriptomic analyses.

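### Stool for two primary endpoints is carried for up to 1 hour with no cooling, stabiliser or time stamps specified, leaving a possible handling effect that pairing does not fully remove

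*Combined protocol and SAP*

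**What the plan says.** Section 2.1 lists "Fecal metabolome as determined by targeted metabolite profiling" and "Fecal microbiota as determined by 16S rRNA and metatranscriptomic analyses". Section 10.1 puts both under primary endpoints, the second as "Fecal microbiota profiling by 16S rRNA analysis & metatranscriptomics". The remaining primary endpoint there is circulating metabolites in blood.

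The stool procedure is in section 10.0. The study team supplies a sterile container for the sample, which is "then placed into an opaque brown paper bag and brought to the Division of Nutrition Suite student health services within 1 hour". Storage at -80°C follows. The same written procedure applies at all three collections (end of baseline, end of high protein, end of low protein). For the journey, the text names no cold pack, cooler or stabilising medium. It does not say when the hour starts, sets no limit between arrival and freezing, and asks for no times. The mentions of a cooler and refrigeration are struck through, and they concerned holding the stool after arrival.

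Cooling is written down for other material in the same section. For blood after the draw, "samples will be kept at 4°C until picked up". For take-away meals, "Food for the rest of the day will be provided in an insulated bag containing frozen cold packs".

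Section 4.1 fixes the order of diets for everyone and makes each person their own control. Section 16.1 names a test (paired t) for circulating amino acids only, and 16.2 gives a power statement for plasma amino acids only.

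**The concern.** Until stool is frozen or stabilised, living bacteria in it can go on transcribing genes, breaking down residual protein and using free amino acids. Transcripts and fecal amino acids could therefore move between passage and freezing. As written, the procedure lets the delay vary between one person's samples and leaves no record of it.

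At stake is how a high-versus-low difference in stool is read. Part of it could be noise from unequal delays. Part could be bias, if more substrate is left in stool after 2 g/kg/day than after 0.8 g/kg/day, or if participants deliver faster or slower as the weeks pass. Delay and temperature cannot be reconstructed once the samples are in the freezer.

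**Working it through.** **1. The plan's own figure.** Inputs from 16.2: 10 completers, a difference of 0.996 SD, 5% significance, paired t-test (two-sided assumed, since sidedness is not stated). Noncentrality = 0.996 × √10 = 3.150 with 9 degrees of freedom. The exact noncentral-t power is 80.0%, so the figure reproduces. Enrolment also reproduces: with 4 of 14 lost, 10 / (1 - 4/14) = 14. Both figures concern plasma, and neither depends on stool handling.

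**2. What pairing removes.** For one person, let the handling shift in a stool measurement be s = r × d, where d is the delay to freezing and r the rate of change in the container (linear for simplicity). Then:

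observed high-minus-low difference = true difference + (r_H × d_H - r_L × d_L)

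- Same rate, same delay: the extra term is 0 and the shift cancels.
- Same rate, delays differ at random: the extra term is r × (d_H - d_L). It averages to 0 but adds variance. The text allows any journey up to 60 minutes, so d_H - d_L can reach 60 minutes in either direction from the journey alone.
- Same rate, delays drift over the study: the term has mean r × mean(d_H - d_L). Low protein always follows high protein, so this is confounded with diet.
- Rate depends on substrate: with equal delays the term is (r_H - r_L) × d. It does not cancel, and adjusting for delay does not remove it. Only a smaller r or a smaller d reduces it.

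**3. Size.** The documents give no data on RNA or metabolite stability, so r is unknown. One illustration of the noise, assuming handling adds a share f to the variance of a paired stool difference: noncentrality becomes 3.150 / √(1 + f), and the difference detectable with 80% power becomes 0.996 × √(1 + f).

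| f (assumed) | Power at 0.996 SD, n = 10 | Detectable difference, in original SDs |
|---|---|---|
| 0 | 80% | 0.996 |
| 0.10 | 76% | 1.045 |
| 0.25 | 71% | 1.114 |
| 0.50 | 63% | 1.220 |

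This borrows the plasma effect size, because the plan gives none for stool.

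**4. What chilling could do.** If reaction rates follow a Q10 rule, cooling from about 25°C to 4°C slows them by Q10^((25 - 4)/10) = Q10^2.1. That is 4.3-fold for Q10 = 2 and 10-fold for Q10 = 3. All of these inputs are assumed, and the factor applies only once the sample is cold, so the gain within an hour is smaller.

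**5. Number of samples.** 14 enrolled × 3 collections = 42 stools, or 10 × 3 = 30 from completers.

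**The case against.** The strongest reply has four parts.

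- **The text is silent rather than adverse.** A reader might infer that the stool is uncooled and unstabilised. The documents say only that it goes in a sterile container supplied by the study team and then in a paper bag. What else the kit holds is not described, and participant instructions may cover it. The supported statement is that no cooling or stabiliser is specified. That is still a gap, because the template for section 10 asks for enough detail to replicate the study.
- **The design already helps.** The 1-hour limit is itself a control, the procedure is identical at each collection, and a constant shift largely cancels. Section 11.2 allows about 30 to 60 minutes per occasion for stool delivery and blood draw together, which suggests, without proving, that an hour in transit is a ceiling. This stands for constant shifts. It does not answer unequal delays, drift or a diet-dependent rate.
- **Large effects are easy to assert.** A reader might apply a decay model. With assumed transcript half-lives of 5, 10, 20 or 60 minutes, stools carried 15 and 60 minutes would differ by 45/half-life = 9, 4.5, 2.25 or 0.75 log2 units. The documents support no such figure. The model assumes no new synthesis in bacteria that are still alive. It also works in absolute amounts, whereas losses common to all transcripts largely cancel in relative abundance. So wide a range shows that the size is unknown.
- **The comparators differ.** Blood at 4°C is held after the draw, and meals are kept for the rest of the day. Neither is a short specimen journey. This stands. They show only that cooling is practical here and is written down where it is planned.

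**Conclusion.** The point holds as a weakness in how the stool endpoints are collected. Followed as written, section 10.0 permits a variable and possibly diet-dependent delay effect in metatranscriptomics and fecal metabolites, and leaves no record by which to detect or adjust for it.

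Its size cannot be computed from the documents. The fall in power to between 76% and 63% rests on an assumed 10% to 50% increase in variance. The bias route rests on two conditions that the documents do not establish: more residual protein in stool after the high protein phase, or drift in delivery habits.

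A reader might go further and conclude that the stool assays measure the container more than the gut, or that metatranscriptomics should lose its primary status. Neither follows, because the mechanism is plausible but neither shown nor sized. The plasma amino acid endpoint, which carries the only named test and the only power statement, is unaffected, and no change in sample size follows. The point is worth acting on before the first stool is collected, because the remedy is cheap and the information cannot be recovered later.

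**What to change.** In section 10.0:

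1. Have the participant place the stool container at once in a separate insulated pouch with frozen cold packs, of the type already used for meals. This is the step that reduces a diet-dependent shift, which delay adjustment cannot do.
2. Define the hour as starting at passage, and record times of passage, arrival and freezing at each of the three collections. Arrival and freezing need separate times because 10.0 runs two delivery places together, 12.1 and 17.10 name Student Health Services, and 17.6 puts the freezer in another building. Reconcile these places in the same edit.
3. In 16.1, add a check of whether delay differs between diet phases, and a delay-adjusted fecal high-versus-low comparison. Label the latter a sensitivity analysis only: with about 10 pairs, regressing the paired difference on the within-person difference in delay leaves 10 - 2 = 8 degrees of freedom.

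Optionally, add a small RNA-stabiliser aliquot taken at passage for metatranscriptomics. Its downside is that this portion cannot be used for metabolites and is not the portion used for 16S. If no stabiliser is used, report the ambient or chilled delay as a limitation of the metatranscriptomic result.

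Cost: about 42 pouches, up to 42 tubes if the option is taken, one line of participant instruction and three time stamps per collection. No extra visit or participant is needed.
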